7. SELECTION, DISCONTINUATION AND WITHDRAWAL OF STUDY SUBJECTS

7.1. Inclusion Criteria

Subjects are required to meet the following inclusion criteria:

1. Informed consent in writing from parent(s) or other legally acceptable representative(s) and assent from subject (if appropriate according to local requirements).
2. Male or female 1 to 17 years of age, inclusive.
3. Suspected hematogenous SA osteomyelitis in a large bone (upper or lower extremities, pelvis) based on clinical findings and radiology results.
4. One to three sites of osteomyelitis with expectation that transition to oral antibiotics will be likely prior to discharge to complete IV therapy (The second or third site might be contiguous like a proximal tibia and distal femur but could also be at sites unrelated such as a distal femur and pelvic bone).
5. Female subjects who have reached menarche must have a negative urine pregnancy test.
6. Female subjects who have reached menarche and are sexually active must be willing to practice sexual abstinence or dual methods of birth control (eg, condom or diaphragm with spermicidal foam or gel) during treatment and for at least 28 days after the last dose of any study drug.
7. Sufficient IV access to receive medication.

7.2.Exclusion Criteria

Subjects must NOT meet any of the following exclusion criteria. Septic arthritis contiguous to the site of osteomyelitis is not an exclusion criterion.

1. Received more than 24 hours of IV antibiotics prior to enrollment.
2. More than three bones infected.
3. Disseminated infection or is admitted to the pediatric intensive care unit.
4. Underlying condition (excludes mild eczema or reactive airways disease).
5. Suspected venous thrombosis or concern for endocarditis.
6. Requirement for other reasons for another antibiotic potentially active against organisms commonly causing osteomyelitis in children.
7. Creatinine clearance < 50 mL/min/1.73m² (calculated by the Schwartz formula)
8. AST or ALT > 3 times the upper limit of normal.
9. Neutropenia (<500 neutrophils/mm³)
10. Thrombocytopenia (<50,000 platelets/mm³)
11. Females who are currently pregnant or breast feeding.
12. Hypersensitivity reaction to any Beta-lactam antibiotic
13. Has had an allergic reaction to ceftaroline in the past.

7.3.Prior and Concomitant Treatment and Medications

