7.8. Premature Discontinuation From Study Drug Administration

7.8.1. Discontinuations Due to Safety

Assessments and Procedures: A subject who is prematurely discontinued from study drug administration (ie, before the anticipated full course of study drug required for effective treatment of hematogenous SA osteomyelitis *for safety reasons*) should have EOIV or EOT (if on PO drug) assessments conducted per Section 9, and undergo subsequent assessments at FU, if possible. The same procedures will be followed if the subject needs to continue home IV therapy to complete treatment because the subject is intolerant of an appropriate oral antibiotic or there is no oral agent that is active against the organism isolated.

Clinical Outcome Assessment:

If a subject prematurely discontinues the study drug due to an SAE and requires alternative non-study antimicrobials for hematogenous SA osteomyelitis, the subject should be assessed indeterminate.

Reasons: Reason(s) for premature discontinuation from study drug administration *due to safety* may include, but are not limited to, the following:

- Occurrence of an SAE that, in the opinion of the Investigator, warrants the subject's permanent discontinuation from the study drug or oral drug administration.
- Known pregnancy or breastfeeding during the drug administration period. A female subject whose pregnancy test is positive at the end of total treatment must be followed through the immediate postnatal period or until termination of the pregnancy. Every pregnancy will be reported as soon as possible (within 24 hours of learning of the pregnancy), as described in Section 11.1.4.

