7.8.2. Discontinuations Due to Insufficient Therapeutic Effect

Assessments and Procedures: A subject who is prematurely discontinued from study drug administration *due to insufficient therapeutic effect* should have EOIV (if on IV study drug) or EOT (if on PO drug) assessments conducted per Section 9, and undergo subsequent safety assessments at the 4 to 6 week follow up visit. If a subject is discontinued from IV study drug administration *due to insufficient therapeutic effect* and is switched to an alternative IV antibiotic, the alternative therapy should be recorded.

Clinical Outcome Assessment: A subject who is prematurely discontinued from study drug administration *due to insufficient therapeutic effect* should be assessed as a clinical failure on the day of discontinuation. Such a subject will be automatically assigned an outcome of clinical failure at all subsequent evaluation time points.

Reasons: Reason(s) for discontinuation from study drug administration *due to insufficient therapeutic effect* may include, but are not limited to, the following:

- Clinical Worsening: A subject who shows signs of clinical worsening may be prematurely discontinued from study drug administration at any time. If the Investigator deems the benefit-to-risk ratio of continuing study drug acceptable, study drug administration for at least 48 hours is encouraged before discontinuation. If the subject is improving clinically but the blood cultures are persistently positive for *S. aureus* for up to 5 days, ceftaroline can be continued at the discretion of the investigator.
- Lack of Clinical Progress: For a subject who is stable, yet does not show signs of improvement, the Investigator is encouraged to continue study drug administration at least 48 hours before such a subject is assessed as a clinical failure and the subject is prematurely discontinued from study drug.

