7.8.3. Withdrawal

Assessments and Procedures: A subject may withdraw from the study, or be withdrawn at the request of their parent(s) or legally acceptable representative(s), the Investigator, or Sponsor. A subject who is withdrawn completely from this study during study treatment should be encouraged to undergo, if possible, EOIV (if on IV study drug) or EOT (if not on IV study drug) assessments per Section 10, respectively, on the day of withdrawal.

Clinical Outcome Assessment: A subject withdrawn from the study who is not assessed as a clinical failure should be assessed as indeterminate at all subsequent outcome evaluation time points.

Reasons: Reason(s) for withdrawal from the study may include, but are not limited to, the following:

- Withdrawal of assent or consent
- Lost to follow up
- Significant subject noncompliance, defined as refusal or inability to adhere to the prescribed dosing or

- follow-up regimen
- Investigator determination that it is in the best interest of the subject to withdraw from the study, due to reasons other than an SAE.

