7.10. Stopping Rules

The incidence or severity of AEs indicates a potential health hazard to subjects. The study will be stopped if treatment failures occur in two patients or severe adverse events that are due to ceftaroline in the opinion of the PI occur in two patients.

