current application, as amended. For example, under this definition, hepatic necrosis would be unexpected (by virtue of greater severity) if the investigator brochure referred only to elevated hepatic enzymes or hepatitis. Similarly, cerebral thromboembolism and cerebral vasculitis would be unexpected (by virtue of greater specificity) if the investigator brochure listed only cerebral vascular accidents. "Unexpected," as used in this definition, also refers to adverse events or suspected adverse reactions that are mentioned in the investigator brochure as occurring with a class of drugs or as anticipated from the pharmacological properties of the drug, but are not specifically mentioned as occurring with the particular drug under investigation.

Emergency room visits that do not result in hospitalization (ie, an overnight stay) should be evaluated for one of the other serious outcomes to determine if they qualify as SAEs.

Preplanned hospitalizations (eg, elective procedures for preexisting conditions that did not worsen) are excluded from SAE reporting.

Study endpoints (eg, mortality or major morbidity) must be reported to FDA by the Sponsor as described in the protocol and ordinarily would not be reported under paragraph (c) of the CFR § 312.32. However, if a serious and unexpected AE occurs for which there is evidence suggesting a causal relationship between the drug and the event (eg, death from anaphylaxis), the event must be reported under CFR § 312.32(c)(1)(i) as a serious and unexpected suspected adverse reaction even if it is a component of the study endpoint (eg, all-cause mortality).

The new regulations require that "study endpoints (eg, mortality or major morbidity) must be reported according to the protocol instead of as IND safety reports except when there is evidence suggesting a causal relationship between the drug and the event."

Any worsening of hematogenous SA osteomyelitis under study because of lack of therapeutic effect of any study drug (reported within study endpoints reporting time frame) is captured as an efficacy endpoint and is, therefore, excluded from SAE reporting, unless the event is considered related to the drug.

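### Section 7.8.1 codes an SAE-driven antibiotic change as indeterminate without asking whether the infection caused the SAE, and no rule says whether 7.8.1 or 7.8.2 prevails when both fit

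*Combined protocol and SAP*

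**What the plan says.** Section 7.8 assigns the clinical outcome according to why study drug was stopped.

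- **7.8.1 (safety).** The rule covers any child who "prematurely discontinues the study drug due to an SAE and requires alternative non-study antimicrobials for hematogenous SA osteomyelitis, the subject should be assessed indeterminate". The cause of the SAE plays no part.
- **7.8.2 (insufficient effect).** The subject "should be assessed as a clinical failure on the day of discontinuation", and that code applies at every later time point. Clinical worsening is a listed reason: "A subject who shows signs of clinical worsening may be prematurely discontinued from study drug administration at any time".
- **7.8.3 (withdrawal).** A withdrawn subject "who is not assessed as a clinical failure should be assessed as indeterminate at all subsequent outcome evaluation time points".

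Three other sections bear on the same children.

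- **7.10:** "The study will be stopped if treatment failures occur in two patients or severe adverse events that are due to ceftaroline", in the PI's opinion, occur in two patients. Treatment failure is not defined there.
- **10.3:** the section addresses "Any worsening of hematogenous SA osteomyelitis under study because of lack of therapeutic effect of any study drug". It says that such an event "is captured as an efficacy endpoint and is, therefore, excluded from SAE reporting, unless the event is considered related to the drug". The same section makes an event serious if it prolongs an existing hospital stay.
- **12.7:** the study is halted if two subjects do not improve as expected. This trigger is not tied to the 7.8 codes.

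Sections 12.5 and 12.8 do not say how an indeterminate outcome enters an efficacy proportion.

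**The concern.** These children are inpatients, so a serious complication of the infection that arises on ceftaroline will usually meet an SAE criterion. Section 7.2 shows the kind of event. It excludes at entry disseminated infection, intensive-care admission and "Suspected venous thrombosis or concern for endocarditis". If such a complication develops on treatment and the antibiotic is changed, the wording of 7.8.1 fits and the code is indeterminate. If the investigator instead records clinical worsening, 7.8.2 fits and the code is failure. The same child can receive either code, and the choice may be made once the course is known.

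That choice is informative, because the children concerned are among the sickest. With 18 treated children, one or two codes change the reported efficacy visibly and can decide whether a count of two failures is reached. A child coded indeterminate for an event not attributed to ceftaroline may be counted under neither limb of 7.10.

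Infection-related death is a separate omission: section 7.8 gives it no outcome code.

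**Working it through.** **1. The plan's own figure.** Section 6.2 gives N = 18 for an A'Hern single-stage design with H0: π ≤ 0.50, H1: π ≥ 0.80, type 1 error 0.05 and 80% power. For each n, take the smallest r with P(X ≥ r | n, 0.50) ≤ 0.05, then compute P(X ≥ r | n, 0.80).

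| n | r | alpha | power |
|---|---|---|---|
| 16 | 12 | 0.0384 | 0.798 |
| 17 | 13 | 0.0245 | 0.758 |
| 18 | 13 | 0.0481 | 0.867 |

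The first n with at least 80% power is 18, so the figure reproduces. Section 6.2 does not say which response π measures, and section 12 plans no test of it. The p-values below are therefore illustrative.

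**2. Where the rules overlap.**

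| Event on ceftaroline, antibiotic changed | 7.8.1 wording fits | 7.8.2 wording fits | Code |
|---|---|---|---|
| Drug toxicity that is an SAE | yes | no | indeterminate |
| Osteomyelitis worsens from lack of effect | normally not (10.3 treats it as efficacy) | yes | failure |
| Serious complication beyond the original bone | yes | arguable | not determined |
| Infection-related death | no | no | none given |

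Only the last two rows are unresolved.

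**3. Effect on efficacy.** The documents give no rate for such events, so these are assumed scenarios. Intervals are exact (Clopper-Pearson) 95%.

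- 15 successes, 1 failure, 2 indeterminates. Left out: 15/(18 − 2) = 15/16 = 94% (69.8 to 99.8). Counted as non-success: 15/18 = 83% (58.6 to 96.4).
- 12 successes, 4 failures, 2 indeterminates. Left out: 12/16 = 75.0% (47.6 to 92.7), P(X ≥ 12 | 16, 0.50) = 0.038, which meets the n = 16 cut-off of 12. Counted as non-success: 12/18 = 66.7% (41.0 to 86.7), P(X ≥ 12 | 18, 0.50) = 0.119, below the n = 18 cut-off of 13.

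These counts ignore any early stop under 7.10.

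**4. Effect on a count of two failures.** Assume 7.10 counts only children coded clinical failure. Let q be the true failure rate and m the share of true failures coded indeterminate, both assumed. With q′ = q(1 − m):

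P(at least 2 in 18) = 1 − (1 − q′)^18 − 18q′(1 − q′)^17

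For q = 0.10, m = 0: 1 − 0.15009 − 0.30019 = 0.550. For q = 0.10, m = 0.5, so q′ = 0.05: 1 − 0.39721 − 0.37631 = 0.226.

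| q | m = 0 | m = 0.25 | m = 0.5 |
|---|---|---|---|
| 5% | 22.6% | 14.5% | 7.3% |
| 10% | 55.0% | 39.6% | 22.6% |
| 20% | 90.1% | 77.6% | 55.0% |

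**The case against.** A reader might infer that the worst failures systematically drop out of the failure count, that neither limb of 7.10 can see them, and that efficacy is therefore biased upward. The documents do not support that reading, for four reasons.

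- **The main route to failure exists.** Section 7.8.1 concerns stopping for safety. Section 7.8.2 lists clinical worsening at any time, does not confine it to the original bone, and says its reasons are not exhaustive. An investigator could reasonably place septic deterioration or a new bone focus there. Section 10.3 points the same way. This stands, and it narrows the gap to events that fit both sections.
- **Withdrawal is already handled.** Section 7.8.3 yields to an existing failure assessment. This stands; no change is needed there.
- **Stopping does not rest on the code alone.** Section 7.10 does not link treatment failure to 7.8, 12.7 halts on two children who do not improve, and under 6.4 the DRC receives all SAEs, deaths and discontinuations due to AEs. This mitigates but does not close the gap. Section 12.7 sits in the PK analysis without a link to 7.8 or 7.10, and could miss a child who improves before a complication. The protocol gives no numerical trigger for DRC review.
- **No text removes indeterminates from the denominator.** An indeterminate child does not count as a success under 6.1, so with all 18 retained the result is 15/18 under either code. This stands, and makes the bias conditional.

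Efficacy is also secondary and largely descriptive. The primary objective is safety, where these SAEs and any deaths are reported whatever the efficacy code. In the first scenario, three failures among 18 children would sit uneasily with a stop at two unless they occurred late in enrollment.

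**Conclusion.** The concern holds in a limited form. Section 7.8.1 has no test of cause, it overlaps with 7.8.2 without a precedence rule, and infection-related death has no efficacy code. A child with a serious complication of the infection can be coded indeterminate by following the text literally, and may then not be counted as a failure in the efficacy results or in 7.10.

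The size is conditional. Two such children change 83% to 94% in the first scenario, but only if indeterminates are left out. If half of true failures were coded indeterminate and 7.10 counted only coded failures, the chance of reaching two would fall from 55.0% to 22.6% at a 10% failure rate, and from 90.1% to 55.0% at 20%. The rates and shares are assumptions. Because 7.8.2 and 10.3 already cover worsening of the osteomyelitis, a smaller share is plausible.

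This does not undermine the primary safety objective. It should be settled before outcomes are known, because the choice of code could otherwise follow the result.

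**What to change.** 1. In 7.8.1, limit indeterminate to SAEs that are neither a manifestation nor a complication of the infection under study.
2. State that 7.8.2 (clinical failure, carried forward) prevails over 7.8.1 when both could apply, and that infection-related death is coded as clinical failure.
3. In 12.5 and 12.8, report efficacy on all treated children with indeterminates counted as non-success, at least as a sensitivity analysis, and give the number of indeterminates at each time point.
4. Reconcile the meaning of treatment failure across 7.8, 7.10 and 12.7. Which meaning should govern a halt is for the sponsor and the DRC; the point here is only that the sections should agree.

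Section 7.8.3 can stay as written. The cost is a few sentences, one eCRF tick-box (SAE is a manifestation or complication of the infection: yes/no) and possibly a slightly lower efficacy figure. Patient care is unchanged.

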7.8.2. Discontinuations Due to Insufficient Therapeutic Effect

Assessments and Procedures: A subject who is prematurely discontinued from study drug administration *due to insufficient therapeutic effect* should have EOIV (if on IV study drug) or EOT (if on PO drug) assessments conducted per Section 9, and undergo subsequent safety assessments at the 4 to 6 week follow up visit. If a subject is discontinued from IV study drug administration *due to insufficient therapeutic effect* and is switched to an alternative IV antibiotic, the alternative therapy should be recorded.

Clinical Outcome Assessment: A subject who is prematurely discontinued from study drug administration *due to insufficient therapeutic effect* should be assessed as a clinical failure on the day of discontinuation. Such a subject will be automatically assigned an outcome of clinical failure at all subsequent evaluation time points.

Reasons: Reason(s) for discontinuation from study drug administration *due to insufficient therapeutic effect* may include, but are not limited to, the following:

- Clinical Worsening: A subject who shows signs of clinical worsening may be prematurely discontinued from study drug administration at any time. If the Investigator deems the benefit-to-risk ratio of continuing study drug acceptable, study drug administration for at least 48 hours is encouraged before discontinuation. If the subject is improving clinically but the blood cultures are persistently positive for *S. aureus* for up to 5 days, ceftaroline can be continued at the discretion of the investigator.
- Lack of Clinical Progress: For a subject who is stable, yet does not show signs of improvement, the Investigator is encouraged to continue study drug administration at least 48 hours before such a subject is assessed as a clinical failure and the subject is prematurely discontinued from study drug.

7.8.3. Withdrawal

Assessments and Procedures: A subject may withdraw from the study, or be withdrawn at the request of their parent(s) or legally acceptable representative(s), the Investigator, or Sponsor. A subject who is withdrawn completely from this study during study treatment should be encouraged to undergo, if possible, EOIV (if on IV study drug) or EOT (if not on IV study drug) assessments per Section 10, respectively, on the day of withdrawal.

Clinical Outcome Assessment: A subject withdrawn from the study who is not assessed as a clinical failure should be assessed as indeterminate at all subsequent outcome evaluation time points.

Reasons: Reason(s) for withdrawal from the study may include, but are not limited to, the following:

- Withdrawal of assent or consent
- Lost to follow up
- Significant subject noncompliance, defined as refusal or inability to adhere to the prescribed dosing or

- follow-up regimen
- Investigator determination that it is in the best interest of the subject to withdraw from the study, due to reasons other than an SAE.

7.9. Replacement of Subjects

Subjects who are withdrawn from study before receiving any amount of study drug will be replaced in order to enroll a total of 18 treated subjects for safety evaluations. Subject numbers will not be reused.

7.10. Stopping Rules

The incidence or severity of AEs indicates a potential health hazard to subjects. The study will be stopped if treatment failures occur in two patients or severe adverse events that are due to ceftaroline in the opinion of the PI occur in two patients.

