4.2.3. Completed Pediatric Studies

One of the 11 Phase 1 clinical pharmacology studies, Study P903-15 "Pharmacokinetics of a Single Dose of Ceftaroline in Subjects 12 to 17 Years of Age Receiving Antibiotic Therapy," was conducted in adolescents.

Study P903-15 was a Phase 1, multicenter, open-label, noncomparative, single-dose study of ceftaroline fosamil in subjects 12 to 17 years of age, inclusive, who were hospitalized and receiving antibiotic therapy for treatment of infections of any type. Subjects received a single IV infusion of ceftaroline fosamil at a dose of 8 mg/kg if weighing < 75 kg (165.4 lb) or 600 mg if weighing 75 kg (165.4 lb) or more. The primary objective was to evaluate the single-dose pharmacokinetics of ceftaroline, the prodrug ceftaroline fosamil, and the inactive M-1 metabolite. The secondary objective was to evaluate the safety of ceftaroline in adolescent subjects.

Nine subjects, 5 male and 4 female subjects with a mean age of 13.7 years (range 12 to 16 years), were enrolled in the study. One subject was prematurely discontinued from study drug due to infusion site extravasation that was moderate in severity and assessed by the Investigator as unrelated to ceftaroline. This subject received approximately 80% of the planned dose.

The remaining 8 subjects each received a complete dose of ceftaroline fosamil. All subjects completed the study and were included in the Safety Population. Eight treatment-emergent adverse events (TEAEs) occurred in 5 subjects. All TEAEs were mild or moderate in severity. Three TEAEs (extrasystoles, vomiting, and "electrocardiogram [ECG] prolonged QT interval") were considered related to ceftaroline by the Investigator and each occurred in a different subject. All TEAEs resolved except for "ECG prolonged QT interval" in 1 subject that was detected on Study Day 2 and was not assessed further. (The subject's QTcB and QTcF values were < 450 msec and similar between the predose and postdose measurements.) One subject mentioned above prematurely discontinued study drug, but no subjects prematurely withdrew from the study or died. One subject with osteomyelitis had a serious adverse event (SAE) of a pathologic fracture of the humerus that occurred 13 days after infusion of ceftaroline fosamil. The fracture was mild in severity and considered by the Investigator as unrelated to ceftaroline.

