7.7. Subject Discontinuation or Withdrawal

Subjects should be encouraged to complete all study outcome assessments. However, a subject may be discontinued from study drug or may withdraw assent/consent to participate in this study at any time without penalty or loss of benefits to which the subject is otherwise entitled. Subjects will be assessed for safety of ceftaroline at the time points outlined in the schedule of evaluations, if possible.

7.7.1. Off Study Criteria:

- Subjects who require continued home parenteral antibiotics will be discontinued from the study.
- Subjects that require IV treatment after switching to Oral drug.
- If a subject's estimated CrCl decreases to < 50 mL/min during the treatment period, the subject will be discontinued from the study.
- Diarrhea (the occurrence of > 4 loose stools /day) with blood or mucus
- Moderate to severe maculopapular rash that does not resolve following administration of diphenhydramine (Benadryl®) or any urticarial rash.
- Absolute neutrophil count < 500 WBC/mm³ (Grade 4)
- Hemolytic anemia Grade 2 (evidence of > 2 g decrease in hemoglobin but does not require blood transfusion) or above.
- Thrombocytopenia-Platelet count < 100,000/mm³ (Grade 1)
- AST/ALT > 3 X ULN (grade 3)

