10.2. Causality and Severity Assessments

The causality assessment must be recorded on the appropriate AE CRF. Causal relationship must be assessed by answering the following question:

Is there a reasonable possibility the study drug caused the event?

Yes: There is evidence to suggest a causal relationship between the study drug and AE, ie.:

- There is a reasonable temporal relationship between the study drug and the event, and
- The event is unlikely to be attributed to underlying/concurrent disease, other drugs, or other factors, and/or
- Positive de-challenge and/or re-challenge exist

No: There is no evidence to suggest a causal relationship between the study drug and AE, ie.:

- There is no reasonable temporal relationship between the study drug and the event, or
- The subject did not take the study drug, or

- The event is likely to be attributed to underlying/concurrent disease, other drugs, or other factors, or
- The event is commonly occurring in the (study) population independent of drug exposure

The Investigator must provide an assessment of the severity of each AE by recording a severity rating on the appropriate AE screen(s) of the subject's eCRF. *Severity*, which is a description of the intensity of manifestation of the AE, is distinct from *seriousness*, which implies a subject outcome or AE-required treatment measure associated with a threat to life or functionality (Section 11.1.2). Severity will be assessed according to the following scale.

Mild:	Minor awareness of signs or symptoms that are easily tolerated without specific medical intervention.
Moderate:	Discomfort that interferes with usual activities and may require minimal intervention.
Severe:	Significant signs or symptoms that are incapacitating with an inability to work or perform routine activities and/or that require medical intervention.

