10.3. Serious Adverse Events/Suspected Adverse Reaction

An adverse event or suspected adverse reaction is considered "serious" if, in the view of either the investigator or sponsor, it results in any of the following outcomes:

- Results in death
- Results in a life threatening adverse event
- Requires in-patient hospitalization or prolongation of existing hospitalization
- Results in persistent or significant disability/incapacity or substantial disruption of the ability to conduct normal life functions
- Is a congenital anomaly/birth defect

Important medical events that may not result in death, be life threatening, or require hospitalization may be considered serious when, based on appropriate medical judgment, they may jeopardize the subject and may require medical or surgical intervention to prevent one of the outcomes listed in this definition. Examples of such medical events include allergic bronchospasm requiring intensive treatment in an emergency room or at home, blood dyscrasias or convulsions that do not result in in-patient hospitalization, or the development of drug dependency or drug abuse.

Suspected adverse reaction means any adverse event for which there is a reasonable possibility that the drug caused the adverse event. For the purposes of IND safety reporting, "reasonable possibility" means there is evidence to suggest a causal relationship between the drug and the adverse event. Suspected adverse reaction implies a lesser degree of certainty about causality than adverse reaction, which means any adverse event caused by a drug.

Unexpected adverse event or unexpected suspected adverse reaction. An adverse event or suspected adverse reaction is considered "unexpected" if it is not listed in the investigator brochure or is not listed at the specificity or severity that has been observed; or, if an investigator brochure is not required or available, is not consistent with the risk information described in the general investigational plan or elsewhere in the

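### The two-patient toxicity stop counts severe rather than serious events, so two ceftaroline-related serious AEs rated mild or moderate would not meet it; one added sentence closes this limited gap

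*Combined protocol and SAP*

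**What the plan says.** Section 7.10 gives two counts that stop the study: treatment failure in two patients, or "severe adverse events that are due to ceftaroline in the opinion of the PI occur in two patients". It opens with a general sentence, "The incidence or severity of AEs indicates a potential health hazard to subjects", which carries no threshold and no action.

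Section 10.2 rates severity as mild, moderate or severe and sets it apart from seriousness, "which implies a subject outcome or AE-required treatment measure associated with a threat to life or functionality". Moderate is "Discomfort that interferes with usual activities and may require minimal intervention". Severe covers incapacitating signs or symptoms and also those needing medical intervention. Section 10.3 defines serious by outcome; one criterion is "Requires in-patient hospitalization or prolongation of existing hospitalization".

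Section 7.8.1 deals with a child who stops study drug because of an SAE: if that child also "requires alternative non-study antimicrobials for hematogenous SA osteomyelitis, the subject should be assessed indeterminate". Clinical failure is assigned under 7.8.2, for insufficient therapeutic effect.

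Oversight is set out in three places. Section 6.4 has the DRC meet regularly to review SAEs, deaths, AE discontinuations and potentially clinically significant laboratory results, under a charter agreed before enrollment that fixes the timing and procedures. Section 10.4 has the DRC follow all SAEs. Section 10.5 sends every SAE to Allergan within 24 business hours, and to the FDA and IRB per regulation or local policy.

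**The concern.** Safety is the primary objective, and the only toxicity count in the protocol depends on an intensity rating. Children on IV ceftaroline are inpatients, so an event of moderate intensity can be serious simply because it lengthens the stay. A second related event of that kind would not stop the study. The failure count need not catch it either, because a child taken off drug for an SAE and given other antimicrobials is indeterminate rather than a failure. The protocol text does not then call for an enrollment hold or an early DRC meeting. Whether enrollment pauses is left to the judgment of those notified and to a charter that is not among the documents.

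**Working it through.** **Step 1: what each provision does with a related serious AE rated moderate.**

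| Provision | Effect |
|---|---|
| 7.10, toxicity count | Not counted; the rating is below severe |
| 7.10, failure count | Not counted if 7.8.1 makes the child indeterminate |
| 7.10, opening sentence | May support a judgment; states no count or action |
| 10.5, SAE reporting | Reported to Allergan, FDA and IRB whatever the rating; DRC not named |
| 6.4 and 10.4, DRC | Reviewed at the next regular meeting and followed; no ad hoc meeting stated |

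The protocol does name one event-based DRC contact, for creatinine clearance below 50 mL/min on treatment (10.9). It is not tied to seriousness.

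**Step 2: the plan's own figure.** The protocol gives no operating characteristics for the toxicity stop. Its one calculated figure is n = 18 (6.2), from an exact single-stage design with rates 0.50 and 0.80, 80% power and type 1 error 0.05. This reproduces: 18 is the smallest n that qualifies, rejecting at 13 or more successes, with exact alpha 0.0481 and power 0.867 (n = 16 gives power 0.798 and n = 17 gives 0.758). It says nothing about the toxicity rule.

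**Step 3: how often the count could be missed.** Inputs: n = 18 (6.2), and the threshold of two patients (7.10). Assumed, because the documents give neither: q, the chance that a child has a related SAE, and s, the chance that such an event is rated severe. Children and ratings are taken as independent, with at most one related SAE per child.

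The number of children with a related SAE is Bin(18, q), and the number with one rated severe is Bin(18, qs). Fewer than two related SAEs implies fewer than two severe ones, so

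P(at least 2 related SAEs, fewer than 2 severe) = P(Bin(18, qs) ≤ 1) − P(Bin(18, q) ≤ 1).

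For q = 0.10 and s = 0.75, qs = 0.075:

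- P(Bin(18, 0.075) ≤ 1) = 0.925^18 + 18 × 0.075 × 0.925^17 = 0.2458 + 0.3587 = 0.6045
- P(Bin(18, 0.10) ≤ 1) = 0.9^18 + 18 × 0.10 × 0.9^17 = 0.1501 + 0.3002 = 0.4503
- Difference = 0.1542

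| q | At least 2 related SAEs | Missed, s = 0.90 | Missed, s = 0.75 | Missed, s = 0.50 |
|---|---|---|---|---|
| 1% | 1.4% | 0.25% | 0.6% | 1.0% |
| 2% | 5.0% | 0.9% | 2.0% | 3.6% |
| 5% | 22.6% | 3.3% | 8.2% | 15.3% |
| 10% | 55.0% | 5.9% | 15.4% | 32.3% |

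The missed chance is zero if all related SAEs are rated severe. The table counts serious events only. Severe but non-serious related AEs also count toward 7.10 and could stop the study on their own, so under these assumptions the missed columns are upper limits.

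**The case against.** The strongest reply is that the severe category already catches most of these events. An event needing medical intervention is severe under 10.2, while moderate allows only minimal intervention. A related event that is life-threatening or prolongs hospitalization will usually need treatment. This stands. It is why the higher values of s are the more plausible ones, and nothing in the documents supports an even split.

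The second reply is that oversight does not depend on the rating. SAEs go to Allergan, the FDA and the IRB, and the DRC reviews them and advises on whether enrollment continues. The charter fixes the timing of DRC meetings and may hold an ad hoc trigger. This also stands. What remains is that the protocol's own count, written to set action in advance, uses a term that excludes some related serious events. If severe is a slip for serious, the text still needs correcting.

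Three stronger readings are tempting, and the documents do not support them:

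- A reader might take the earlier adolescent study (4.2.3) as an example of the gap, since an SAE in a child with osteomyelitis was rated mild. But "The fracture was mild in severity and considered by the Investigator as unrelated to ceftaroline". It shows that seriousness and intensity can diverge, not that a related SAE was rated below severe.
- A reader might infer that children would go on being enrolled unchecked until the next DRC meeting. The interval is not stated, and external SAE reporting is a separate route to action.
- A reader might want a matching trigger for the 7.7.1 removals, such as "Absolute neutrophil count < 500". Those criteria are not mapped to the 10.2 scale, but the investigator may rate such events severe. The DRC already reviews AE discontinuations and significant laboratory values. No rate is given from which to weigh a trigger, and one covering all of 7.7.1 toxicity would take in urticarial rash and Grade 1 thrombocytopenia. That choice can be left to the charter.

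**Conclusion.** The point holds in a limited form. As written, two related serious AEs rated below severe meet neither count in 7.10, and the protocol states no hold or early DRC review in response. Across assumed related-SAE rates of 1% to 10%, the missed chance runs from 0.25% to 5.9% if 90% are rated severe, from 0.6% to 15.4% if 75% are, and from 1.0% to 32.3% if 50% are. These figures illustrate the size and do not estimate it, because both inputs are assumed. The claim concerns the protocol text only; the charter may already cover the case. It is a cheap improvement, and the stopping rule otherwise stands.

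**What to change.** Keep the existing stop and add one sentence to 7.10:

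> If a second subject has a serious AE judged related to ceftaroline, whatever its severity rating, enrollment is held and the DRC is convened ad hoc; enrollment resumes on the DRC's recommendation.

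Mirror it in the DRC charter. The investigator's judgment of relatedness is kept; only the dependence on the severity rating goes. No separate trigger for 7.7.1 removals is proposed.

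The cost is a possible extra DRC meeting and a short hold. At the planned 6 subjects per year (Summary), a one-month hold delays 6/12 = 0.5 child. Children already on ceftaroline are unaffected.

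The new sentence acts beyond the existing stop whenever the first two related SAEs are not both severe, with chance (1 − s²) × P(at least 2), again counting serious events only. At q = 1% this is 0.0138 × 0.19 = 0.3%, × 0.4375 = 0.6% and × 0.75 = 1.0% for s = 0.90, 0.75 and 0.50. At q = 10% it is 0.5497 × 0.19 = 10.4%, × 0.4375 = 24.0% and × 0.75 = 41.2%. These exceed the missed chances because a hold can also come before a stop that is met later.
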